5.1.2. Secondary Objective(s)

The study secondary objectives are as follows:

- 1. To compare subjects that will develop RD versus subjects that will not develop RD (in terms of parameters additional to those needed for primary objective, see Section 5.2.2 for details).
- 2. To characterize the predictive values of etCO₂, RR, SpO₂ and the IPI in predicting RD and ORADE.
- 3. To measure health care utilization costs during the study period.

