4.2 Secondary objectives

4.2.1 Secondary objective 1

To compare subjects that will develop RD versus patients that will not develop RD.

4.2.2 Secondary objective 2

To characterize the predictive values of etCO₂, RR, SpO₂ and the IPI in predicting RD and ORADE.

4.2.3 Secondary objective 3

To measure health care utilization costs during the study period.

5 Investigation Plan

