7.10.2.2 Secondary endpoint#2

The secondary objective#2 will characterize the predictive values of etCO₂, RR, SpO₂ and the IPI⁵ in predicting rORADE. To evaluate the predictive values of the Capnostream monitoring parameters for rORADE, the Sensitivity, Specificity, PPV and NPV will be calculated. rORADE events will be considered the Gold standard and the CS20p monitoring parameters as the measurement to be tested. The population used for this endpoint is PRDPS adjudicated as RD. All Clinical Events occurring during not monitored period will be reported but excluded from the table below. For each RD adjudicated by the CEC, the Capnostream monitoring will be checked if any of the parameter meets at least once the thresholds (RR \leq 6 breaths for \geq 3 minutes, SpO₂ \leq 85% for \geq 3 minutes, EtCO₂ \geq 60 mmHg for \geq 3 minutes or IPI < 3,4,5,6). The table below shows the distribution of the true and false positive and negative for each monitored parameter:

Test		Gold Standard		
Monitoring Parameter		ORADEs/RDs		
RR ≤ 5 breaths for ≥ 3 minutes		YES	NO	Tot
	YES	TP	FP	TP+FP
	NO	FN	TN	FN+TN
	Tot	TP+FN	FP+TN	N
Monitoring Parameter		ORADEs/RDs		
SpO2 ≤ 85% for ≥ 3 minutes		YES	NO	Tot
	YES	TP	FP	TP+FP
	NO	FN	TN	FN+TN
	Tot	TP+FN	FP+TN	N
Monitoring Parameter		ORADEs/RDs		
etCO2 ≤ 15 or ≥ 60 mmHg for ≥ 3 minutes		YES	NO	Tot
	YES	TP	FP	TP+FP
	NO	FN	TN	FN+TN
	Tot	TP+FN	FP+TN	N
Monitoring Parameter		ORADEs/RDs		
IPI <3		YES	NO	Tot
	YES	TP	FP	TP+FP
	NO	FN	TN	FN+TN
	Tot	TP+FN	FP+TN	N
IPI <4		YES	NO	Tot
	YES	TP	FP	TP+FP
	NO	FN	TN	FN+TN
	Tot	TP+FN	FP+TN	N
IPI <5		YES	NO	Tot
	YES	TP	FP	TP+FP
	NO	FN	TN	FN+TN
	Tot	TP+FN	FP+TN	N
IPI <6		YES	NO	Tot
	YES	TP	FP	TP+FP
	NO	FN	TN	FN+TN
	Tot	TP+FN	FP+TN	N
Monitoring Parameter		ORADEs/RDs		
Any Monitoring Parameter RR ≤ 6 breaths for ≥ 3 min or SpO2 ≤ 85% for ≥ 3 min or EtCO2 ≥ 60 mmHg for ≥ 3 min or IPI < 3,4,5,6		YES	NO	Tot
	YES	TP	FP	TP+FP
	NO	FN	TN	FN+TN
	Tot	TP+FN	FP+TN	N

Where:

- N will be all RDs adjudicated by the CEC.
- TP= true positive are all rORADEs and parameter over/below the threshold.
- FN= false negative are all rORADEs but no parameter over/below the threshold.
- FP= false positive are all no rORADE but parameter over/below the threshold.
- TN=true negative are all no ORADEs and no parameter over/below the threshold.

Measure of the accuracy will be:

- Sensitivity: $\{TP/(TP+FN)\}$,
- Specificity: $\{TN/(FP+TN)\}$,
- Positive predictive value: $\{TP/(TP+FP)\}$,

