9.3 Detection Tool

The Detection Tool analyzes each patient's monitoring using an algorithm based on the device episodes thresholds as stated in the primary endpoint. The Detection Tool provides for each patient multiple Episodes. Since there could be multiple episodes in a short time period around each Episode, the Detection Tool is set to aggregate episodes with at most 30 minutes time difference between them in one file. In addition the episodes file consists of time window of 30 min before and after the first and last episode.

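### Secondary endpoint 2 counts a threshold crossing as predicting an rORADE without requiring that it come first, so sensitivity as a measure of prediction may be overstated

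*SAP*

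**What the plan says.** Protocol 5.1.2 gives the second secondary objective as characterizing the monitored parameters "in predicting RD and ORADE", and SAP 4.2.2 repeats it. SAP 7.10.2.2 narrows the target to rORADE and keeps the language of prediction.

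The analysis in that section has these parts:

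- **Reference and test:** "rORADE events will be considered the Gold standard and the CS20p monitoring parameters as the measurement to be tested".
- **Unit:** "N will be all RDs adjudicated by the CEC".
- **Positive test:** for each such RD, "the Capnostream monitoring will be checked if any of the parameter meets at least once the thresholds".
- **Cells:** "TP= true positive are all rORADEs and parameter over/below the threshold". The other three cells are defined in the same way, by presence or absence only.
- **Timing:** the one rule is "All Clinical Events occurring during not monitored period will be reported but excluded from the table below". It restricts which events enter and does not order crossing and event.

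No look-back window, lead time or before-onset condition appears in SAP 7.10.2.2 or Table 27, in SAP 9.3 and 9.4, or in Protocol 5.2.2 and 13.4.

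**The concern.** A signal predicts an event only if it comes before the event. Protocol 4.1 rests part of its case for capnography on earlier warning. Under the cell definitions, an rORADE whose only crossing of a given parameter occurs during the event or after it is a true positive for that parameter. That crossing could not have warned anyone.

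At stake is the sensitivity column of Table 27, and with it any published statement that a parameter or an IPI cut-off predicts respiratory opioid events. The problem is separate from the restriction of the table to adjudicated RDs: it would remain whichever subjects were included.

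**Working it through.** **1. Is there a figure to reproduce?** No. Neither document states an expected sensitivity, crossing frequency or rORADE count for this endpoint. The question is one of definition, so the passages come first and an illustration follows.

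**2. Which stretch of monitoring is searched?** The SAP does not say. There are two readings.

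- *Whole record.* Monitoring runs for up to 48 hours (SAP 5.3). A crossing at any time in it, including well after the rORADE, makes the test positive.
- *The RD's own Episode-File.* SAP 9.3 merges episodes at most 30 minutes apart and adds a "time window of 30 min before and after the first and last episode". A crossing during the rORADE still counts. A later one can too: the event may fall in the 30 minutes before the first episode, or one parameter may cross before the event and another only after it within the same merged file. SAP 9.4 also sends clinical events to the CEC when there is no device episode, and for those this reading leaves the search period undefined.

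The 30-minute tail adds little. A further episode at the detection thresholds within 30 minutes would have been merged, so the tail matters only for IPI, or for RR if the cut-off of 6 in the text of 7.10.2.2 is used in place of the detection cut-off of 5.

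**3. Direction for sensitivity.** The denominator, rORADEs in monitored time, is the same under either rule. Those with a crossing before the event are a subset of those with a crossing at any time. Before-event sensitivity is therefore less than or equal to the any-time figure.

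**4. Direction for PPV.** Let π be the share of adjudicated RDs with an rORADE, and let an uninformative parameter cross with probability q in both columns. Then PPV = πq / [πq + (1 − π)q] = π. Lowering q equally in both columns leaves PPV at π; lowering it only in the rORADE column reduces PPV. The result depends on the rule for RDs without an rORADE, and no index time is defined for them. The same gap leaves the direction for specificity open.

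**5. Illustrative size for sensitivity.** Assume that crossings follow a Poisson process unrelated to the event, that event time is uniform over the monitored period and that monitoring continues after the event. With any-time probability q, Λ = −ln(1 − q), and the before-event probability is 1 − q/Λ.

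| q (any time) | Λ | Before event | Gap (points) | Share of hits only after |
|---|---|---|---|---|
| 20% | 0.223 | 10.4% | 9.6 | 48% |
| 40% | 0.511 | 21.7% | 18.3 | 46% |
| 80% | 1.609 | 50.3% | 29.7 | 37% |

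**6. If little monitoring follows the event.** With the event at a fixed fraction f of monitored time, the before-event probability is 1 − (1 − q)^f. For q = 50%, f = 0.5 gives 29.3%, so (50 − 29.3)/50 = 41% of hits are later ones. With f = 0.9 it is 46.4%, or 7% of hits. At f = 1 the share is zero.

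**The case against.** The strongest reply is that this is a diagnostic-accuracy table whose wording is loose. Protocol 5.2.2 speaks of correlating predictive value with the occurrence of RD and ORADE, and the SAP sets a test against a gold standard. On that view the any-time table is legitimate and only the label is wrong. This stands in part: the table is usable as a measure of co-occurrence, and it would be too strong to infer that the endpoint yields nothing.

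Other limits also stand:

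- A reader might infer that a crossing on the following night is counted. That needs the whole-record reading. The section works per RD, and the Episode-File reading is at least as natural.
- A reader might infer that PPV is inflated. Step 4 shows that this does not follow.
- A reader might infer that looser cut-offs suffer more. In the illustration the gap in points grows with the crossing rate, but the share of hits after the event falls.
- Monitoring may end on leaving the ward (Protocol 9.6), and Protocol Appendix A lists ICU transfer, invasive ventilation and arrest among anticipated events. Many rORADEs may leave little later record.
- The charted event time arises under usual care with the study screen blinded and alarms silenced (Protocol 9.6), so it may be the time of discovery.

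The CEC Charter and the Statistical Programming Requirements document were not available and could contain a time rule, but 7.10.2.2 refers to neither for one. None of this supplies the missing order.

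**Conclusion.** The point holds for sensitivity. As written, 7.10.2.2 allows crossings during an rORADE to count as predicting it on either reading of the search period. It allows later crossings too, most clearly if the whole record is searched. Predictive sensitivity can only be overstated or unchanged. For PPV and specificity no direction can be given.

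The size cannot be derived from the documents. It lies anywhere from near zero, if monitoring ends at the event, to roughly 37% to 48% of hits for an uninformative parameter crossed in 20% to 80% of cases. The upper end assumes uniform event time, continued monitoring and crossings unrelated to the event, and is not an estimate for this study.

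The endpoint is secondary and descriptive, and the primary risk score is unaffected. The change should still be made, because the planned analysis does not support a label of prediction.

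**What to change.** In SAP 7.10.2.2:

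1. State which stretch of monitoring belongs to each RD, including clinical events with no device episode.
2. For rORADEs, report each parameter's sensitivity in two parts: crossings that start before the recorded event time (or the first rescue action, if earlier), and cases whose crossings start only at or after it. Give the lead time for the first part, and use that part alone for any statement about prediction.
3. Label the any-time 2×2 tables, and the specificity, PPV and NPV in Table 27, as concurrent detection (co-occurrence). Do not impose a look-back on RDs without an rORADE. They are identified largely by the crossing itself, so they have no independent index time, and a look-back would turn false positives into true negatives and raise specificity artificially.
4. State as a limitation that the charted event time may lag true onset.

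The cost is SAP wording and programming. Protocol 11.2 already collects the date and time of the event and of rescue-related actions, and the Detection Tool's 30-minute windows require timed device data. The downside is a lower reported predictive sensitivity.

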7.10.1 Primary endpoint

The primary endpoint that will be used to derive and validate the risk score assessment is the RD episode, defined as a clinical diagnosis made after reviewing monitoring data in conjunction with the clinical data and consistent with accepted pathophysiologic mechanisms. The primary endpoint used to derive the score will be the occurrence of RD episodes captured by continuous capnography and pulse oximetry measurements recorded on the Capnostream device memory data in conjunction with the clinical data as reported by the Investigators. RD determination will be validated by an independent Clinical Event Committee (CEC). The CEC will use both clinical data and monitor parameters specified below as a guideline; if determination of an RD episode is clinically appropriate but outside of the guidelines a rationale will be provided. Data suggestive of an RD episode include any of the following:

RR ≤ 5 breaths for ≥ 3 minutes
SpO2 ≤ 85% for ≥ 3 minutes

etCO ₂ ≤ 15 or ≥ 60 mmHg for ≥ 3 minutes
Apnea episode lasting > 30 seconds
Any respiratory Opioid-Related Adverse Event (rORADE)

The assessment of RD episodes will be made by the analysis of the Capnostream and clinical data for each patient. For each patient all potential RD episodes will be derived using the Detection Tool (see section 9.3) and will be submitted to the CEC according to a Priority List (see section 9.4) in order to adjudicate the potential RD episodes starting from RD episodes most likely to be RD. The CEC adjudication will stop the adjudication at the first RD occurring per patient (all details on CEC process are reported in the CEC Charter version 3.0).

All potential RD episodes in the study will be always rated by 3 coders (see detail in the Clinical Events Committee Charter Template, Version 3.0).

Patients of the MFAS will be randomly assigned (2:1) into respectively the derivation and the validation cohort. In case of low enrollment rate or low episode rate or according the outcome of a preliminary assessment of the events per variable or unbalanced enrollment per site/country the MFAS could not be randomized but used for model building and the bootstrap method, deriving 500 computer-generated samples by random selection with replacement for model validation³ (see section 9.2 for details).

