9.4 Priority List

The CEC will stop the adjudications at the first RD for each patient, while they will adjudicate all Clinical Events. In order to optimize CEC time the following priority list will be used to prioritize some Episode-File to be review first:

Priority 1: all clinical events with/without any episode from device data. In case multiple Clinical events per patient the CEC will review them using the time of occurrence, from first clinical event to the last.

Priority 2: Multiple episodes involving at least two parameters among SpO₂, EtCO₂, RR and Apnea. In case of multiple Episode-Files with this priority the CEC will review first the Episode-Files with the higher number of Episodes within the Episode-Files.

Priority 3: Multiple Episodes of the same parameter. In case of multiple Episode-Files with this priority the CEC will review using this order: SpO₂, EtCO₂, RR and Apnea

Priority 4: Any overnight Episodes of the same parameter. In case of multiple Episode-Files with this priority the CEC will review using this order: SpO₂, EtCO₂, RR and Apnea

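### Secondary endpoint 2 tabulates CEC-adjudicated RDs, but the CEC's stop-at-first-RD rule caps and selects the rows without an rORADE, so specificity, PPV and NPV in Table 27 partly reflect that rule

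*SAP*

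**What the plan says.** SAP 7.10.2.2 evaluates etCO2, RR, SpO2 and IPI against rORADE: "rORADE events will be considered the Gold standard and the CS20p monitoring parameters as the measurement to be tested". The row of each 2x2 table is an adjudicated RD. The text reads "For each RD adjudicated by the CEC, the Capnostream monitoring will be checked if any of the parameter meets at least once the thresholds", and under the tables "N will be all RDs adjudicated by the CEC". True positives and false negatives are rORADEs with and without a crossing. The other column is RDs that are not rORADEs; for example, "FP= false positive are all no rORADE but parameter over/below the threshold". Clinical events outside monitored time are left out. Table 27 then reports sensitivity, specificity, PPV and NPV.

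Which RDs reach the table is decided elsewhere. SAP 9.4 says: "The CEC will stop the adjudications at the first RD for each patient, while they will adjudicate all Clinical Events". SAP 7.10.1 repeats the stopping rule: "The CEC adjudication will stop the adjudication at the first RD occurring per patient". The review order in 9.4 is:

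- Priority 1: clinical events.
- Priority 2: "Multiple episodes involving at least two parameters among SpO₂, EtCO₂, RR and Apnea", taking the file with most episodes first.
- Priorities 3 and 4: same-parameter files, in the order SpO2, EtCO2, RR, Apnea.

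SAP 9.3 expects the Detection Tool to return several episodes per patient. Neither 7.10.2.2 nor 9.4 adds weights, a patient-level definition or a caveat.

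**The concern.** The stopping rule suits the primary analysis, which needs only whether a patient had at least one RD (SAP 7.10.1.1). It does not suit a table whose rows are RDs.

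The two columns are filled by different rules. Every clinical event in monitored time is adjudicated, so every rORADE enters, several per patient if they occur. A device-only RD enters at most once per patient, and not at all once that patient's clinical event has been called an RD. The one that enters is the first confirmed in a queue sorted by how many and which parameters crossed, which is the test result being evaluated.

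This is separate from restricting the population to confirmed RDs. Even for a question posed only among RDs, the table would not describe the RDs that occurred. PPV and NPV depend on the ratio of the two columns, and specificity depends on which files were confirmed first. Three of Table 27's four measures would then carry a rule written to save committee time.

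**Working it through.** **Scale.** The plan gives no figure for this endpoint. Its sizing is 120 / 0.12 = 1000 for derivation, 1000 / (2/3) = 1500 evaluable and 1500 × 1.10 = 1650 enrolled, which reproduces. At 12%, 1500 subjects give 180 with RD.

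**What follows without assumptions.** Compare the planned table with one in which every file had been adjudicated. TP and FN are the same in both, so sensitivity TP/(TP+FN) is unchanged. The counted FP and TN are subsets of all FP and all TN. Therefore:

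- PPV = TP/(TP+FP) can only stay equal or rise.
- NPV = TN/(TN+FN) can only stay equal or fall.
- Specificity = TN/(FP+TN) is not moved by the cap alone, because one RD drawn at random per patient keeps the same expected crossing share. It moves because the order is not random.

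**Illustration for SpO2.** The following are assumptions; the documents supply none of them:

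- Of the 180 RD patients, 20 have one rORADE each and 160 have only device RDs.
- SpO2 sensitivity is 80%, so TP = 16 and FN = 4.
- Each RD file crosses SpO2, etCO2, RR and apnea independently with probabilities 0.2, 0.2, 0.2 and 0.5, given at least one crossing.
- Files per patient are 1 + Poisson, and the CEC confirms the first file reviewed.

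Over all files, the SpO2 crossing share is 0.2 / (1 − 0.8³ × 0.5) = 0.2 / 0.744 = 0.269. FP is 160 × files × 0.269. As selected, the share comes from simulating the 9.4 order, and FP is 160 × that share.

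| Mean files | Specificity, all → selected | FP, all → selected | PPV, all → selected | NPV, all → selected |
|---|---|---|---|---|
| 1.5 | 73% → 70% | 64.5 → 48.0 | 20% → 25% | 98% → 97% |
| 2 | 73% → 65% | 86.0 → 56.0 | 16% → 22% | 98% → 96% |
| 3 | 73% → 59% | 129.0 → 65.6 | 11% → 20% | 99% → 96% |
| 5 | 73% → 54% | 215.1 → 73.6 | 7% → 18% | 99% → 96% |

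For two files: PPV over all files is 16/(16+86) = 15.7%, and as selected 16/(16+56) = 22.2%. NPV over all files is 234/(234+4) = 98.3%, and as selected 104/(104+4) = 96.3%. If every patient had exactly one RD file, nothing would change.

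**Other parameters.** Further scenarios used 1.5 to 6 files per patient, three parameter mixes and four degrees of multi-parameter overlap. Specificity fell for SpO2 and the any-parameter row in every scenario and fell or stayed flat for etCO2. RR had no fixed sign. With three files and common multi-parameter files, RR specificity went from 0.62 to 0.56. With six files, an equal mix and few multi-parameter files, it went from 0.75 to 0.81, because RR-only files queue behind SpO2 and EtCO2. IPI, four of Table 27's seven columns, was not simulated.

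**Other comparators, two files per patient.**

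- One random RD per patient: FP = 160 × 0.269 = 43, so PPV = 16/(16+43) = 27%. The planned 22% is then lower.
- One row per patient over the same device-only RD patients, threshold met in any file: SpO2 specificity is about 55%. The planned figure of about 65% is then higher.

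**The case against.** The strongest objection concerns the unit of analysis. The section says "The population used for this endpoint is PRDPS adjudicated as RD"; PRDPS is a set of patients (SAP 7.1.3), and the check is made on the Capnostream monitoring rather than on an Episode-File. If the sponsor means one row per RD patient with the whole recording examined, it does not matter to specificity which file the CEC confirmed first. That reading is possible, but the definition of N and the wording of the check count RDs. The SAP must state the unit in either case.

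A reader might go further and infer that the plan biases PPV up and specificity down for every parameter. The documents do not support that. The PPV and NPV directions hold only relative to all RDs that occurred, a comparator that counts repeated files from one patient, and the signs reverse against the alternatives shown. The specificity direction is not settled for RR or IPI. The documents give no file counts, crossing probabilities or rORADE numbers, so the percentages illustrate a mechanism and do not estimate a bias.

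A reader might also infer that every rORADE in the study is counted. Only those in monitored time are. Nor does the point reach the primary analysis, where stopping at the first RD loses nothing.

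**Conclusion.** The point holds as a defect in the plan as written. On the row definition in 7.10.2.2, the no-rORADE column is capped at one device-only RD per patient and chosen by parameter, while the rORADE column is complete for monitored periods. Specificity, PPV and NPV in Table 27 therefore partly reflect the stopping rule; sensitivity does not.

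Relative to all RDs, the PPV and NPV directions are algebraic. The specificity directions (down for SpO2 and any-parameter, down or flat for etCO2, open for RR and IPI) rest on simulation. The size is unknown: across the assumed 1.5 to 5 files per patient, SpO2 specificity shifts by about 3 to 19 points and PPV by about 5 to 11. The conclusion rests on the event-level reading and on patients often having more than one RD file. It warrants a change to this secondary endpoint; the sample size and primary endpoint are untouched.

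**What to change.** In SAP 7.10.2.2, replace the statement of N with one row per monitored MFAS subject. Set any adjudicated rORADE during monitoring (yes/no) against each parameter threshold, including the IPI cut-offs, met at least once during monitoring (yes/no). Compute the crossings from the stored device memory data. The word monitored is needed because SAP 7.1.3 keeps subjects in the MFAS even if monitoring never starts.

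If the table of CEC-confirmed RDs is kept, label it a priority-selected sample and report only sensitivity from it.

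Tabulating all Episode-Files not linked to an rORADE would not repair the problem. Each file exists because a device threshold was crossed (SAP 9.3), so a negative for one parameter is merely a file triggered by another.

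The cost is SAP wording and some programming on raw device data, with no extra CEC review. Detection Tool output may not suffice: it uses the primary-endpoint thresholds, which contain no IPI and use RR ≤ 5, while 7.10.2.2 uses RR ≤ 6 in places and RR ≤ 5 in others. Those RR entries must be reconciled first. The main limitation is that a per-subject table does not link a crossing in time to the event.
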